Multicenter observational program VAP-PRO-C3

Protocol nº IC4-05682-055-RUS

NCT03722836

Evaluation of the efficacy and safety of vasoactive drugs as a part of combination treatment, and its influence on the general outcomes of treatment of patients with chronic venous edema (CEAP class C3) in real clinical practice.

01\09\2018

1

Background

An edema takes a special place among clinical manifestations of varicose veins of the lower extremities. Its occurrence suggests about significant hemodynamic disorders, the consequence of which is a cascade of pathological reactions at the microcirculatory and molecular levels.^{1,2} Clinical significance of this sign of the disease is illustrated by the fact that such a widely known term as "chronic venous insufficiency" (CVI) is applied already at the occurrence of venous edema (CEAP class C3).³ For several decades, the pathogenetic aspects of venous edema, as well as the issues of treatment of CVI patients have been a subject of active investigations worldwide. To date, the mechanisms leading to the development of edema have been explored,⁴ the complex of measures for treating patients with C3 clinical class was established, and the efficacy of such a treatment was confirmed. At the same time, studies in CVI are ongoing, and many problems still await their solution. In particular, one of them relates to a search for an optimal method of diagnosis and conservative treatment of the disease.

References

- 2. Handbook of venous disorders. Guidelines of the American Venous Forum (third edition). Edited by P. Gloviczki. Hodder Arnold 2009; ISBN -978-0-340-938-805.
- 3. Coleridge Smith Ph.D. Microcirculation in Venous Disease (second edition). LANDES bioscience 1998; ISBN- 1-57059-476-7.

Design

The VAP-PRO-C3 is a multicenter observational program, which is carried out in the frame of routine consultations and follow-up of patients. The program includes patients with chronic venous diseases (CVDs) of CEAP class C3. It is scheduled in Russia for 2018-2019. The program is expected to enroll 90 phlebologists from 60 cities of Russia. The planned number of patients is 1350.

First visit of the first patient:	01\10\2018

examination of patients with CEAP class C3 of CVD. Particular attention will be paid to determining the changes of edema using the routine methods (geometric method of a truncated cones and duplex ultrasound scanning).

Treatment

The observational nature of the program assumes that all examinations, procedures and changes in the therapy of a patients, including changes in doses of drugs, should be carried out only on the basis of the decision of attending physician and in full accordance with the current guidelines for management of a particular type of patients under investigation, instructions for medical use of the drugs, as well as in the settings of routine practice.

The treatment is carried out in full accordance with the current guidelines. Participation of a patient in the program, as well as his/her refusal to continue participation, should not affect the current treatment, the availability of diagnostic procedures, or the amount and quality of other necessary medical care. Names and doses of drugs used for the CVD treatment, as well as changes in the doses will be recorded in the CRF.

Inclusion criteria:

- Age 18 years old or above
- Written informed consent
- Patient did not receive treatment with venoactive drugs within the past 4 weeks prior to the inclusion in the study
- Diagnosis of chronic venous disease of class C3 (CEAP)
- Doctor plan to prescribe VADs

Exclusion criteria:

- Age below 18 years old
- Written informed consent is not obtained
- History of alcohol or drug abuse or use of narcotic drugs
- History of allergic reaction to diosmin or any other venoactive agent, or their intolerance
- History of allergic reaction to anesthetics and/or sclerosing agents
- Chronic venous disease of CEAP class C0-C2 or class C4-C6
- Lymphatic edema of the lower extremities
- Secondary varicose veins, angiodysplasia, or neoplasia
- Arterial disease (ankle-brachial index <0.9)
- Infection within the past 6 weeks
- Any of the following concomitant diseases, which can affect the results:
 - o Connective tissue disease (including rheumatoid arthritis), arthritis
 - Heart failure
 - o Chronic kidney disease
 - o Intermittent claudication (peripheral artery disease)
 - o Diseases of the bones or joints of the lower extremities
 - o Malignant growth

- Treatment with drugs potentially causing leg edema (calcium channel blockers, hormonal drugs, NSAIDs, etc.)
- History of deep vein thrombosis (within the past year)
- History of superficial thrombophlebitis (within the past 3 months)
- Patient cannot walk (regardless of the cause)
- Predictable poor adherence to treatment
- Participation of the patient in the intervention study within the previous 3 months
- For women: pregnancy or breastfeeding, the desire to become pregnant within at least 2 months after the study
- Patient cannot attend a follow-up visit
- Patients with a contraindication to diosmin-containing agents, including Detralex

Criteria for the assessment of treatment efficacy

- 1. Venous clinical severity score (VCSS).⁵
- 2. Clinical class of CVD according to CEAP classification.⁶
- 3. Changes in the severity of CVD symptoms (leg heaviness, pain, swelling, night cramps and itching), as assessed by the **visual analogue scale (VAS)**.⁷
- 4. Changes in the severity of edema, as assessed by the method of truncated cones⁸ and duplex ultrasound scanning.
- 5. Changes in the quality of life, as assessed by the CIVIQ-14 questionnaire.⁹
- 6. Satisfaction with treatment, as assessed by the **Darvall self-administered** questionnaire. 10

References

- 6. Российские клинические рекомендации по диагностике и лечению хронических заболеваний вен. Савельев В.С., Покровский А.В., Затевахин И.И., Кириенко А.И. и др. Флебология. 2013;7(2):2-47. [The Russian clinical guidelines for the diagnosis and treatment of chronic venous diseases. Savelyev VS, Pokrovsky AV, Zatevakhin II, Kirienko AI et al. Flebologiya. 2013;7(2):2-47. (In Russ.).]
- 7. Huskisson E.C. Measurement of pain. *Lancet* 1974; 2:1127-1131.
- 8. Lennihan R.Jr, Mackereth M. Calculating volume changes in a swollen extremity from surface measurements. *Am J Surg.* 1973 Nov;126(5):649-52.

PLAN OF THE STUDY

Procedure V0 visit	V1 visit	V2 visit	V3 visit	V4 visit
--------------------	----------	----------	----------	----------

	(Inclusion)	(at 2 weeks)	(at 1 month)	(at 2 months)	(at 3 months)
Informed consent form	+				
Patient's questionnaires	+				+
Completion of the CRF	+	+	+	+	+
VCSS	+				+
CEAP	+				+
Data on the treatment and its change	+	+	+	+	+
Registration of AEs		+	+	+	+
Assessment of edema by the method of truncated cones	+	+	+	+	+
Assessment of edema by duplex ultrasound scanning (DUS)	+				+
Detralex 500 mg 2 times per day 1000 mg daily (1 tablet or 1 sachet)	+	+	+	+	+
Compression hosiery, topical treatment	Compression therapy can be administered on discretion of investigator at any visit				
Surgical intervention	Surgery can be performed on discretion of investigator at any visit				

Safety considerations

1. Definitions

1.1 Pharmacovigilance information

Pharmacovigilance data include any unintended or adverse event associated with the use of a medicinal product in humans, whether or not considered drug related, including the following **special situations** (situations where no adverse event occurred but information needs to be collected):

- exposure during pregnancy or breastfeeding;
- overdose, abuse, misuse, off-label uses, medication error, occupational exposure (including professional one);
- lack of the treatment efficacy of drug.

1.2. Adverse event (AE)

Adverse event (AE) is any untoward medical occurrence in a patient or clinical-trial participant who received the medicinal product, which does not necessarily have a causal relationship with the use of this medicinal product.

An adverse event can therefore be any unfavourable and unintended sign (e.g. an abnormal laboratory finding), symptom, or disease temporally associated with the use of a medicinal product, whether or not considered as related to the medicinal product.

1.3. Adverse (drug) reaction (ADR)

Adverse reaction (synonyms: Adverse drug reaction, Suspected adverse (drug) reaction, Adverse effect, Undesirable effect) is a response to a medicinal product which is noxious and unintended.

"Response" in this context means that a causal relationship between a medicinal product and an adverse event is at least a reasonable possibility.

Adverse reactions may arise from use of the product within or outside the terms of the marketing authorization or from occupational exposure. Conditions of use outside the marketing authorization include off-label use, overdose, misuse, abuse and medication errors.

1.4. Serious adverse (drug) reaction (SADR)

Serious adverse reaction is an adverse reaction, which results in death, is life-threatening, requires in-patient hospitalisation or prolongation of existing hospitalisation, results in persistent or significant disability or incapacity, or is a congenital anomaly/birth defect.

Life threatening in this context refers to a reaction in which the patient was at risk of death at the time of the reaction; it does not refer to a reaction that hypothetically might have caused death if more severe.

Medical and scientific judgement should be exercised in deciding whether other situations should be considered serious reactions, such as important medical events that might not be immediately life threatening or result in death or hospitalisation but might jeopardise the patient or might require intervention to prevent one of the other outcomes listed above.

Examples of such events are intensive treatment in an emergency room or at home for allergic bronchospasm, blood dyscrasias or convulsions that do not result in hospitalisation or development of dependency or abuse.

Any suspected transmission via a medicinal product of an infectious agent is also considered a serious adverse reaction.

2. Responsibilities

2.1. Events to be reported

All available information about the following events reported during the study will be recorded:

- All serious adverse drug reactions related to the use to Detralex
- All non-serious adverse drug reactions related to the use to Detralex
- All reports about special situations (see 1.1)
- All adverse events

2.2. Responsibilities of investigator

In prospective studies, at medical visits the investigator will ask a participating patient to indicate whether or not an adverse event (serious or not) has occurred.

Investigator has to assess causal relationship between an adverse event and the investigated drug intake, as well as the seriousness criteria and later on the outcome of the event.

In case of Adverse Events, Adverse Drug Reactions or special situations that occurs during the study (both serious and non-serious), the investigator must complete the "Adverse event / Adverse drug reaction / Special Situation Reporting Form" (Appendix 1) without waiting for the clinical outcome or the results of additional investigations.

If the event is serious, it will be notified immediately (same or next working day at the latest) to Servier company in Russia via e-mail to address [contact] or by fax to

number [name]. The anonymized copies of all the available and relevant laboratory findings, hospitalisation reports or other investigation results performed in connection with the adverse event should be attached to the form.

All other events should be reported by investigator within 2 working days.

The same rules apply for the transferring of additional information about the event.

The investigator must ensure the appropriate follow-up of the patient depending on the nature of event, until it resolves. The investigator will continue to notify follow up data according to timeframes defined above.

If investigator does not follow-up a patients anymore (i.e. in case of hospitalisation followed by the treatment by specialist or the participant's general practitioner,...), he/she will do every effort to contact the specialist or department in charge of follow-up of the patient, so as to have additional information and report it to Servier company in Russia.

2.3. Responsibilities of sponsor/marketing authorization holder (MAH)

Independently of the regulatory obligations of investigator, the sponsor/MAH must report the pharmacovigilance data to the appropriate authorities in accordance with the Good Vigilance Practice and local regulations.

Cases are closed when an adverse event has recovered or patient's condition was stabilized and the report is deemed sufficiently detailed for adequate medical analysis of the case.

Statistical parameters

Statistical analysis:

Baseline characteristics will be analyzed in all included patients despite adherence to the protocol. Analysis of the results of program will be performed using the SPSS 12.0 software package (SPSS Inc., USA). The data entry errors will be corrected before the statistical processing. Quantitative parameters will be presented, depending on the distribution of raw data, as arithmetic mean \pm standard deviation for parametric variables, or as median (25; 75 percentiles) for nonparametric variables. Multiple comparisons will include adjustments for continuity.

Changes in the quantitative parameters during the follow-up period will be evaluated using the Student's t-test for paired samples or its nonparametric analogue, Wilcoxon test. Differences on the quantitative parameters, both between the independent groups and during the follow-up, will be evaluated as the mean difference with the corresponding 95% confidence interval.

Intergroup comparisons of changes in VAS scores, global index of CIVIQ questionnaire, Darvall index, and an integral score of the edema severity will be carried out using two-factor analysis of variance (ANOVA) with repeated measures to compare the scores before and after the treatment.

Safety will be assessed in the intention-to-treat population (all patients who received at least one dose of Detralex during the study).

Adverse events will be recorded and analyzed in patients with the reporting of all the AEs, SAEs, ADRs, SADRs and special situations.

Patient's expectations and satisfaction with the treatment

After adjustments for the confounding factors (gender, age, CEAP class, Detralex treatment, type of procedure), subgroup analyzes will be conducted to determine the effect of these variables on expectations and whether there are significant differences for them using the chi-square test. When analyzing data, a common linear model (the SPSS software feature) will be used.

Ethical considerations

The study will be conducted in accordance with the principles of the Declaration of Helsinki, as amended in Fortaleza, Brasil, in 2013.

Patients will be fully informed, and they will need to provide a written consent before participation in the program. The doctor should confirm in the CRF that the patient has provided an informed consent. The "Informed consent" also implies individual discussion with the patient in their national language about the nature and content of the interview and examination to be conducted.

Confidentiality of patient data will be guaranteed by the use of identification (ID) numbers. The relation between ID number and patient's identity will be known only to investigators, which will ensure the anonymity of patients.

Data collection

Please inform patients about their participation in this survey using the patient information sheet attached to this file. All the CRFs that you completed will be sent to Servier. Data anonymity is guaranteed.

Results

The data you obtained will be used to prepare the study reports under supervision of independent scientific experts.

Publications of results

Before being sent for publication, any manuscript, containing the results of the present study, should be provided to Servier company for reviewing. Servier company reserves the right to ask for modifications if needed.

Adverse event / Adverse drug reaction / Special Situation Reporting Form*

104-03	002-			r.com, or pas	•			6 or by email to y.
Year of birth	or	Age	Gender	r	Height	Weight	P	atient's ID:
	or M/F							
Description of	f adve	erse evei	nt/reaction/sp	ecial situatio	n:	Date of ev	vent onset	Date of event termination (in case of recovery)
□ Ho □ Per □ Co	ath e threa spitali rsisten ngenit	☐ YES	prolongation of ficant disability ly/birth defect nt event		alisation	structur Not yet No reco Death Unknov	red with cons ral or function recovered overy	equences (persistent nal impairment)
Causal relation NO If «Yes», plea If «No» or «N	nship use inco	with in YES licate da	take of invess NOT tes of the use p, please speci	tigational dru Γ APPLICABI of investigation	ig: □□ LE onal drug in t e adverse evel	he first line o	of the table l	netory, hospital reports, below: ated to the medication
of Servier com ☐ NO ☐ ☐	pany YES					of Servier co	ompany:	
List of o			Daily dose / route of administration	D from	ates of intake to	e:	Indication	
					-			
					-			
					-			

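### The only rule for multiple comparisons is a continuity adjustment, which cannot control error across tests, and no alpha, primary outcome or other procedure is stated

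*Combined protocol and SAP*

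**What the plan says.** All references are to the combined protocol and SAP.

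- **Multiplicity rule** (Statistical parameters, Statistical analysis): "Multiple comparisons will include adjustments for continuity". Nothing else in the text addresses multiple comparisons.
- **Outcomes** (Criteria for the assessment of treatment efficacy): six numbered criteria, none called primary. The third, "Changes in the severity of CVD symptoms (leg heaviness, pain, swelling, night cramps and itching"), covers five VAS symptoms. The fourth has two edema methods, truncated cones and duplex ultrasound. The sixth begins "Satisfaction with treatment, as assessed by the" and names the Darvall questionnaire.
- **Within-patient tests** (Statistical analysis): Student's "t-test for paired samples or its nonparametric analogue, Wilcoxon test".
- **Intergroup tests** (same place): "Intergroup comparisons of changes in VAS scores, global index of CIVIQ questionnaire, Darvall index, and an integral score of the edema severity", by two-factor ANOVA "with repeated measures to compare the scores before and after the treatment". The groups are not named.
- **Subgroup tests** (Patient's expectations and satisfaction with the treatment): five factors, "gender, age, CEAP class, Detralex treatment, type of procedure", examined for their effect on expectations and "whether there are significant differences for them using the chi-square test".
- **Level**: no alpha or sidedness is given. The nearest item is the 95% confidence interval promised for mean differences.

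**The concern.** The named remedy does not do the job assigned to it. A continuity correction improves the approximation when one discrete statistic, such as a 2x2 chi-square or a Wilcoxon rank sum, is referred to a continuous distribution. It is the same whether one test is run or fifty, and it does not exist for a t-test or an ANOVA F-test.

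This is a wrong rule rather than a missing detail. An analyst who follows it runs every test at its own nominal level while the report can say that multiple comparisons were adjusted. With no primary outcome, level or family, nothing says which result carries the efficacy conclusion. The plan is not purely descriptive either, since it tests for significance in several places.

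**Working it through.** The plan states no alpha, power or family-wise error rate, so it has no figure of its own to reproduce. The finding rests on the text; the arithmetic below only shows scale.

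**1. Counting the baseline (V0) to month-3 (V4) tests.** From the efficacy criteria: VCSS 1, VAS symptoms 5, truncated-cone volume 1, ultrasound thickness 1, CIVIQ-14 1, giving 9. Adding either CEAP class or the Darvall index gives 10; adding both gives 11. Ten is used for illustration.

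**2. Chance of at least one false positive.** Assumptions: two-sided 0.05 per test, and no true change on any outcome.
- Independent tests, 1 − 0.95^k: k = 9, 0.370; k = 10, 0.401; k = 11, 0.431.
- Equally correlated normal statistics, by numerical integration:

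| k | correlation 0.5 | correlation 0.9 |
|---|---|---|
| 9 | 0.269 | 0.124 |
| 10 | 0.287 | 0.128 |
| 11 | 0.304 | 0.131 |

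**3. What a continuity correction does where it applies.**
- *Wilcoxon signed-rank, no ties.* SD = √(N(N+1)(2N+1)/24), and the shift in z is 0.5/SD. For an assumed N = 900, SD = 7800.7 and the shift is 0.000064. At z = 1.96, p moves from 0.0499958 to 0.0500033. At the planned N = 1350 the shift is smaller still, 0.000035.
- *2x2 chi-square.* With an assumed 675 per group (half of 1350) and counts 338 against 374, χ² = 3.852 and p = 0.0497 uncorrected; corrected, χ² = 3.641 and p = 0.0564. With 450 per group and counts 225 against 254, p moves from 0.0527 to 0.0614.

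So the correction is negligible for Wilcoxon but can carry a single chi-square result across 0.05. That is still not control across tests. By exact enumeration with 100 to 675 per group and event rates of 0.3 or 0.5, the type I error of one corrected test is 0.035 to 0.044. Five independent tests of that kind still give 1 − (1 − 0.035)^5 ≈ 0.16 to 1 − (1 − 0.044)^5 ≈ 0.20.

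**4. What a real adjustment would change within patients.** The smallest change detectable with 80% power, in SDs of the change, is (z for α/2 + 0.842)/√N. At N = 1350, √N = 36.74:
- α = 0.05: (1.960 + 0.842)/36.74 = 0.076.
- First Holm step for 10 tests, 0.05/10 = 0.005: (2.807 + 0.842)/36.74 = 0.099.
- First Holm step for 11 tests, 0.05/11 = 0.00455: (2.838 + 0.842)/36.74 = 0.100.

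Dropout is not counted.

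**5. Intergroup and subgroup tests.** Their number cannot be derived. The ANOVA grouping is not named, and the expectation items tested by chi-square are not listed. CEAP class is one of the five factors, yet only class C3 is eligible at baseline. Detralex treatment is another, yet the Plan of the study table marks Detralex at every visit.

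**The case against.** **It is an observational program, so strict error control is optional.** This stands, and a fully descriptive analysis is accepted as a fix below. The plan also already promises mean differences with 95% confidence intervals. But as written it promises an adjustment and looks for significant differences, so it has not taken the descriptive route.

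**The sentence may be a translation slip for multiplicity.** Possible. Even so, no method, level or family would be named, and the same edit is needed.

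**The main results would hardly change.** Largely true. The 40% figure needs no true change on any outcome and independence between outcomes, both extreme, and Holm would alter only within-patient conclusions that rest on very small changes.

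Four stronger readings are tempting but not supported:
- *That the plan carries a 40% false-positive risk.* The documents give no level, and correlated outcomes bring the figure down to 13% at correlation 0.9.
- *That a family-wise error can be put on the intergroup and subgroup tests.* Any such figure needs an assumed grouping and an assumed number of chi-square tests.
- *That a continuity correction never matters at this sample size.* That is true for Wilcoxon only.
- *That the ANOVA gives a second p-value for the same efficacy question.* It is introduced as an intergroup comparison of changes, so its natural target is group by time. Duplication arises only if its time effect is also read as an efficacy test.

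**Conclusion.** The point holds. The plan's one rule for multiple comparisons cannot control error across tests, and the available text supplies no alpha, primary outcome or other procedure in its place. This conclusion follows from the wording and needs no assumption.

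Its size is moderate. For ten V0 to V4 tests the illustrative family-wise error runs from 13% to 40% depending on correlation, given the assumed level and no true change. The practical effect on within-patient conclusions is small, about 0.02 SD in the detectable change at 1350 patients (0.099 − 0.076 = 0.023). The exposure is mainly in the intergroup and subgroup tests, where groups are smaller and the number of tests is open. The plan should be corrected, but the defect does not invalidate the program.

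**What to change.** Make one of two wording changes in Statistical parameters.

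**Option A, descriptive.** Delete the sentence. State that no primary outcome is designated and that all analyses are descriptive. Report effect estimates with 95% confidence intervals: mean differences for quantitative parameters, differences in proportions for categorical ones. Remove the wording about significant differences from the subsection on expectations and satisfaction. This is the shorter option and suits an observational program.

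**Option B, confirmatory family.** Replace the sentence with:

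> V0–V4 changes in VCSS, CEAP class, five VAS symptoms, truncated-cone limb volume, DUS thickness, CIVIQ-14 and the Darvall index form one family of 11 paired tests, adjusted by the Holm procedure at an overall two-sided 0.05; no single outcome is primary. The integral edema score, V1–V3 changes, intergroup comparisons and subgroup analyses are exploratory and reported as estimates with 95% confidence intervals without claims of significance. Continuity correction is used only where a discrete statistic is approximated by a continuous distribution.

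Under B, the wording about significant differences in the expectations subsection must be amended to match. The family includes the Darvall index because the Plan of the study table schedules patient questionnaires at both V0 and V4 and the ANOVA already compares that index before and after treatment.

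**Cost.** Wording only, with no new data; Holm can be applied by hand to SPSS p-values. Under B some p-values become less favourable: with 11 tests the detectable within-patient change rises to at most 0.100 SD at 1350 patients. Under either option, intergroup and subgroup results can no longer be called significant.

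### The expectations and satisfaction paragraph specifies an analysis of expectations only, adjusts for and tests the same five variables, and gives the significance test to chi-square, which does not adjust

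*Combined protocol and SAP*

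**What the plan says.** The combined protocol and SAP, section Statistical parameters, ends with a paragraph headed "Patient's expectations and satisfaction with the treatment". Its first sentence opens with "After adjustments for the confounding factors (gender, age, CEAP class, Detralex treatment, type of procedure" and continues that "subgroup analyzes will be conducted to determine the effect of these variables on expectations". The same sentence names the method that is to decide significance: "whether there are significant differences for them using the chi-square test". A second sentence adds: "When analyzing data, a common linear model (the SPSS software feature) will be used". No dependent variable, covariate list or link function is given for that model.

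Elsewhere in the document:

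- Criteria for the assessment of treatment efficacy, item 6, is "Satisfaction with treatment, as assessed by the" Darvall questionnaire. Expectations are not a listed criterion. The study cited for the questionnaire has a title that refers to expectations before, and satisfaction after, a venous procedure.
- Statistical parameters places the Darvall index among the "Intergroup comparisons of changes in VAS scores, global index of CIVIQ questionnaire, Darvall index, and an integral score of the edema severity", to be compared before and after treatment by two-factor repeated-measures ANOVA. No confounders are listed.
- Plan of the study marks patient questionnaires at V0 and V4, without saying which items are asked when. It marks Detralex from V0 onward, and on surgery it states: "Surgery can be performed on discretion of investigator at any visit".
- Inclusion and exclusion criteria admit only CEAP class C3 and require that venoactive treatment is already planned.

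**The concern.** This is a non-randomised programme in which the physician chooses the treatment. Covariate adjustment is the main protection against reporting patient selection as an effect, so the plan has to say which outcome is modelled, on which covariates, and which test decides.

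Here the only outcome named is expectations, while the efficacy criterion is satisfaction. The list of confounders is also the list of effects, so it is unclear which variable is the exposure at any point. The sentence promises adjustment and then assigns significance to a test that does not adjust. Followed literally, the report would carry unadjusted p-values presented as adjusted effects, and nothing in the plan would oblige anyone to produce an adjusted estimate for satisfaction.

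Time order is a further difficulty. If expectations are recorded at inclusion, an association with a procedure performed later would reflect who goes on to have a procedure, not an effect on expectations.

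**Working it through.** The plan states no figure for this analysis, so there is nothing to reproduce. The check is a reading of the text, followed by one illustration.

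**Step 1: outcome.** The heading names expectations and satisfaction; the analysis sentence names expectations only. The model sentence names neither. The ANOVA includes the Darvall index but lists no covariates and requires a score before treatment. Satisfaction with a treatment not yet given has no obvious value at V0, and the plan does not explain the index. No passage names satisfaction as the dependent variable of an adjusted model.

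**Step 2: the five variables, if expectations are taken at V0.**

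| Variable | Status at V0 |
|---|---|
| Gender, age | Known; usable |
| CEAP class | C3 for everyone, so constant; the V4 class comes after the outcome |
| Detralex treatment | Marked from V0; the number of enrolled patients not receiving it, if any, is not stated |
| Type of procedure | May be performed at V0 or at any later visit; not defined further (taken here to mean the surgical intervention in the schedule) |

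**Step 3: the test.** A plain chi-square test compares crude proportions. It also needs age in classes, and the plan gives no cut points, so the information lost by grouping age cannot be quantified from the documents. The linear model can adjust, but the plan does not say how the two results relate or which prevails.

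**Step 4: illustration.** Assumed inputs, none from the documents: one binary confounder present in half the patients; the probabilities of a procedure and of a high expectation are both 0.5 + d with the confounder and 0.5 − d without it; no effect of procedure on expectation; two-sided 5% level; 1000 runs per scenario. Sizes are 90 physicians × 10 patients = 900 (Design and Methodology) and the planned 1350 (Design). The mismatch between the two is a separate matter.

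| d | N | Crude chi-square rejects | Linear model with confounder rejects |
|---|---|---|---|
| 0.05 | 900 | 6.7% | 5.6% |
| 0.10 | 900 | 24.2% | 5.9% |
| 0.20 | 900 | 99.5% | 5.2% |
| 0.05 | 1350 | 6.5% | 5.8% |
| 0.10 | 1350 | 29.3% | 4.8% |
| 0.20 | 1350 | 100% | 4.4% |

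A hand check agrees. The joint probability of procedure and high expectation is ½(½ + d)² + ½(½ − d)² = ¼ + d². With both margins at ½, the crude correlation is d² / ¼ = 4d². At d = 0.10 this is 0.04. For N = 900 the noncentrality is 900 × 0.04² = 1.44, with square root 1.20, so the rejection rate is about P(Z > 0.76) + P(Z < −3.16) = 0.224 + 0.001, or about 22%. For N = 1350 it is 2.16, with square root 1.47, giving about P(Z > 0.49) = 31%. Both are within simulation error of the table.

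**The case against.** The strongest reply is that the paragraph is loosely translated and that the linear-model sentence supplies what is needed. Such a model can adjust, the sentence is not restricted to expectations, and the heading includes satisfaction. This stands in part. A reader might infer that chi-square is the only method planned, or that satisfaction will certainly go without adjustment; the documents support neither. They do support saying that no adjusted analysis of satisfaction is specified and that the respective roles of test and model are left open.

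Timing is the second reply. The questionnaire row does not separate expectation items from satisfaction items, so V0 collection of expectations is an inference from the V0 and V4 marks and the cited title. Surgery may take place at V0, Detralex is marked at V0, and venoactive treatment is already planned at inclusion. A planned treatment can shape what a patient expects. A reader might infer that Detralex and procedure can have no bearing on expectations; that goes too far. Only a procedure performed after expectations were recorded is excluded as a cause. The word effect in this text may also mean no more than association.

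Finally, satisfaction is the last of six efficacy criteria and expectations are not among them, so the point does not threaten the programme as a whole. That stands and limits its weight.

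**Conclusion.** The concern holds in a limited form. The paragraph specifies an outcome that is not the efficacy criterion, uses one list as both adjusters and tested effects, and gives significance to an unadjusted test while leaving the adjusting model undefined. This is more than missing detail, because following the sentence as written produces unadjusted p-values under an adjusted label.

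The size cannot be derived from the documents. The false-positive rates for the crude test, from 6.5% to 100%, depend entirely on the assumed strength of confounding; they show that the choice between test and model can matter, not how much it will matter here. With weak confounding (d = 0.05) it hardly matters.

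The statement about later procedures is conditional on expectations being collected at V0. The statement that CEAP class is constant at V0 follows directly from the eligibility criteria. The point should be corrected before analysis, at moderate priority.

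**What to change.** Rewrite the paragraph as two separately specified analyses.

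1. **Satisfaction.** Make V4 satisfaction the dependent variable of the general linear model already named, or of an ordinal model if answers are ordered categories. List the covariates: gender, age as a continuous variable, the V0 expectation response if collected, co-treatment, and procedure with its timing recorded. Count only procedures performed before the V4 questionnaire. Report adjusted estimates with 95% confidence intervals. Keep Detralex treatment as a covariate only if it varies among the patients analysed.
2. **Expectations.** State the visit at which they are recorded. If this is V0, use only variables known or planned at V0, omit CEAP class because it is constant, and describe the results as associations.

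For both, state that inference rests on the model, and label any chi-square test as an unadjusted description. Say which questionnaire items are asked at V0 and which at V4, and how the Darvall index in the repeated-measures ANOVA is formed.

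The cost is wording and slightly more analysis work on the same data, provided that procedure dates are recorded. Because procedures are chosen during follow-up, their coefficients in the satisfaction model remain associations even after adjustment, and the report should say so.
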